2.4.10 Clinical Procedures and Laboratory Tests

Due to the risk of decreased clearance of pregabalin in participants with moderate to severe renal insufficiency, active surveillance to prevent drug accumulation will be performed. Plasma creatinine will be determined before study enrollment and only patients with a CrCl ≥ 30 [by Cockcroft-Gault formula] will be eligible. If renal insufficiency (CrCl <30 mL/min occurs, the subject will be withdrawn from the study. If CrCl 30-60 mL/min, the maximum dosage will be 300mg/day, per Lyrica® prescribing information.

Concomitant analgesic medications:

- Subjects treated with gabapentin or other anticonvulsant for neuropathic pain will be required to taper down the medication and to discontinue it at least 2 weeks prior to study initiation.
- Patients on antidepressant treatment for pain or depression (TCAs, SSRI, SNRIs etc. will be allowed to continue their medications provided they have been on a stable dose for at least 4 weeks before study initiation. No dose regimen changes of antidepressants will be allowed during the study period. Patients requiring dose regimen changes will be withdrawn from the study.
- Patients on around-the clock opioid treatment (including tramadol) will be allowed to continue their medication provided they have been on a stable dose for at least 4 weeks before study initiation. The maximum allowed dose of opioid will be equivalent to 60mg oral morphine sulphate. Patients with higher doses will be required to taper down their opioid dose to maximum 60mg oral morphine equivalent, and continue it for 4 weeks before enrollment in

the study. PRN short-acting opioids for painful CIPN treatment will not be allowed. Patients receiving PRN short-acting opioids (with or without acetaminophen) for pain other than CIPN will be allowed up to 4 daily doses, with daily recording of analgesic consumption.

- Treatment with NSAIDs will be discontinued at least 2 weeks before study initiation. However, low-dose aspirin (≤ 325 mg/day) will be allowed.

2.4.11 Drug procurement and storage

The study drug (pregabalin 75mg capsules) and a matching placebo will be provided by Pfizer Inc. The study drug and placebo are identical and indistinguishable in terms of physical appearance. Both medications will be stored in an OVCR approved narcotics cabinet in the Human Subjects Study lab in the Department of Anesthesiology. An unblinded research nurse coordinator will maintain the study drug accountability log and be unblinded to study drug assignment. The study drug and placebo will be labeled using subject study initials and Study ID number and dispensed by the unblinded nurse coordinator, who is not involved in any other part of the study and does not otherwise interact with participants during the study. The study drug prescription will include dosage instructions and pager number for the PI and study coordinator.

3.0 MANAGEMENT OF INTERCURRENT EVENTS

3.1 Adverse Experiences

The subjects will be monitored for evidence of adverse events. Patients will be prompted to report seven specific adverse events (somnolence, dizziness, edema, nausea, headache, dry mouth and blurry vision) on their EMA device daily throughout the study period. Patients will be required to report any adverse effects in their daily diary, and to report any potentially serious adverse effects to the study team. All adverse events will be reported and followed until satisfactory resolution. The description of the adverse experience will include the time of onset, duration, severity, etiology, relationship to the study drug (none, unlikely, possible, probable, highly probable), and any treatment required.

As the study drug is supplied by Pfizer and this investigator-initiated trial is supported by Pfizer ASPIRE grant program, any serious adverse events will be reported to Pfizer via the completion of “Investigator-Initiated Research Serious Adverse Report Form”, according to the Safety Reporting Reference Manual.

The assessment, grading, and reporting of Adverse Events (AEs) will be followed according to the guidelines outlined below:

Adverse Events

Definition: any unfavorable medical occurrence in a human subject including any abnormal sign, symptom, or disease.

Grading: the descriptions and grading scales found in the revised NCI Common Terminology Criteria for Adverse Events (CTCAE) version 4.0 will be utilized for all toxicity reporting. A copy of the CTCAE version 4.0 can be downloaded from the CTEP website.

Attribution (relatedness), Expectedness, and Seriousness: the definitions for the terms listed that should be used are those provided by the Department of Health and Human Services' Office for Human Research Protections (OHRP). A copy of this guidance can be found on OHRP's website: <http://www.hhs.gov/ohrp/policy/addevntguid.html>

Unanticipated Problems

Definition:

- unexpected (in terms of nature, severity, or frequency) given (a) the research procedures that are described in the protocol-related documents, such as the IRB-approved research protocol and informed consent document; and (b) the characteristics of the subject population being studied;
- related or possibly related to participation in the research (“possibly related” means there is a reasonable possibility that the incident, experience, or outcome may have been caused by the procedures involved in the research); and
- suggests that the research places subjects or others at a greater risk of harm (including physical, psychological, economic, or social harm) than was previously known or recognized.

Noncompliance

Definition: failure to follow any applicable regulation or institutional policies that govern human subjects research or failure to follow the determinations of the IRB. Noncompliance may occur due to lack of knowledge or due to deliberate choice to ignore regulations, institutional policies, or determinations of the IRB.

Serious Noncompliance

Definition: noncompliance that materially increases risks, that results in substantial harm to subjects or others, or that materially compromises the rights or welfare of participants.

Protocol Exceptions

Definition: A planned deviation from the approved protocol that are under the research team's control. Exceptions apply only to a single participant or a singular situation.

Pre-approval of all protocol exceptions must be obtained prior to the event.

Reporting to the Human Research Protection Office (HRPO) and the Quality Assurance and Safety Monitoring Committee (QASMC) at Washington University

The PI is required to promptly notify the IRB of the following events:

- Any unanticipated problems involving risks to participants or others which occur at WU, any BJH or SLCH institution, or that impacts participants or the conduct of the study.
- Noncompliance with federal regulations or the requirements or determinations of the IRB.
- Receipt of new information that may impact the willingness of participants to participate or continue participation in the research study.

These events must be reported to the IRB within **10 working days** of the occurrence of the event or notification to the PI of the event. The death of a research participant that qualifies as a reportable

event should be reported within **1 working day** of the occurrence of the event or notification to the PI of the event.

All the prescribing information, including clinical pharmacology, adverse effects, pharmacokinetics, dosage forms, storage, stability are included in the attached appendix – Lyrica USPI document.

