2.3.1 Inclusion Criteria

Inclusion criteria:

1. Age >18
2. Distal symmetric pain distribution (both feet, with or without pain in hands).
3. Pain appeared during or up to 12 weeks after treatment with oxaliplatin, paclitaxel, docetaxel or any combination of these.
4. Score of 4 or more on DN4 neuropathic pain questionnaire (Bouhassira, Attal et al. 2005).
5. Pain duration > 2 months.
6. Patient report of average daily pain intensity >3 on 0-10 Numerical Rating Scale (NRS) in the past week.
7. Women of childbearing potential and men must agree to use adequate contraception (hormonal or barrier method of birth control, abstinence) prior to study entry and for the duration of study participation. Should a woman become pregnant or suspect she is pregnant while participating in this study, she must inform her treating physician immediately.
8. Able and willing to sign an IRB-approved written informed consent.

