2.4.3 Study Period

[figure not shown]
The cross-over study design and the treatment plan are illustrated in Figure 1. Pregabalin (or matching placebo) will be administered for four weeks in each period. The target dose will be increased from 75mg BID to 300mg BID within 7 days (per schedule in Fig. 1), and continued for an additional 22 days.

In case of any grade 2 adverse events (Common Terminology Criteria for Adverse Events – CTCAE version 4.0), the dose will be reduced to the last dose prior to dose increase (i.e. to 150mg BID from 300mg BID; to 75mg BID from 150mg BID). If the adverse effect diminishes to \leq Grade 1, one attempt to dose escalate will be allowed after 3 additional days. If the dose escalation is not tolerated (i.e. recurrent grade 2 adverse event), the treatment will be continued at the previous (lower) dose until day 28. Any CTCAE \geq grade 3 will trigger subject withdrawal from the study.

At the end of treatment sequence, the dose will be tapered over 3 days (e.g., 150mg BID for 2 days, then 75 mg BID for 1 additional day) followed by 10 days of study drug-free washout (end of week 6). In subjects with CrCL 30-60 mL/min, the target (maximum) dose will be 300mg/day. In these subjects the dose will be tapered over 3 days of 75mg BID dosing. If subject's highest tolerable maintenance dose was 75mg BID, the taper schedule will be 75mg QD over 3 days.

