3.3 Potential Risks

3.3.1 Potential risks from pregabalin

Potential adverse effects usually associated with pregabalin include dizziness, somnolence, xerostomia, headache, visual disturbances, peripheral edema and abnormal gait (all less than 15% prevalence).

Other common (>10% prevalence) adverse effects may include fatigue, ataxia, tremor and weight gain. Less common (5-10% prevalence) adverse effects reported with pregabalin include abnormal thinking, confusion, euphoria, speech disorder, pain, insomnia and constipation. Rare but potentially serious adverse effects reported with pregabalin use are: angioedema, suicidal thoughts, allergic reaction, infection, hypertension, hypotension, amnesia, hypoglycemia, vomiting, thrombocytopenia, and nystagmus.

Subjects will be educated regarding the possible adverse effects, and these will be monitored through weekly screening of patient-reported diary and weekly telephone follow-ups with the patient.

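### The daily diary asks by name about six of the seven effects that section 3.3.1 calls usual for pregabalin; abnormal gait, and the related ataxia, have no named prompt, so new unsteadiness may be captured somewhat less well

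*Combined protocol and SAP*

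**What the plan says.** Section 3.1 sets the named daily prompts: "Patients will be prompted to report seven specific adverse events (somnolence, dizziness, edema, nausea, headache, dry mouth and blurry vision". It adds an open route: "Patients will be required to report any adverse effects in their daily diary".

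Section 3.3.1 gives the effects usually associated with pregabalin as dizziness, somnolence, xerostomia, headache, "visual disturbances, peripheral edema and abnormal gait (all less than 15% prevalence". It continues: "Other common (>10% prevalence) adverse effects may include fatigue, ataxia, tremor and weight gain". For the effects it lists, it provides patient education and says that "these will be monitored through weekly screening of patient-reported diary and weekly telephone follow-ups with the patient".

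Other parts of the protocol bear on collection:

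- Table 1 marks adverse event assessment as daily in all eight treatment weeks, and again at the final visit.
- Section 2.4.3 (Compliance; Electronic data collection) describes a diary that reminds the patient to complete the adverse event entry until it is done, with data reviewed about weekly.
- Section 2.4.3 (Safety) says that possible adverse events are taken up at the weekly contacts and that patients may contact the team about any event.

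No section names gait, balance or ataxia in a prompt or a call checklist, and Table 1 has no gait or balance assessment.

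**The concern.** The protocol judged six of the usual effects worth asking about by name every day, and it gives no reason for leaving out the seventh. Abnormal gait is also an effect that this population could easily overlook. Inclusion criterion 2 requires "Distal symmetric pain distribution (both feet, with or without pain in hands", so a patient who becomes unsteady on the drug may put it down to the neuropathy. Dry mouth or headache is less open to that confusion.

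The stake is individual safety during a quick titration: "The target dose will be increased from 75mg BID to 300mg BID within 7 days". With reduced renal function the ceiling is lower: "In subjects with CrCL 30-60 mL/min, the target (maximum) dose will be 300mg/day". A grade 2 event lowers the dose (2.4.3), and grade 3 or higher ends participation (3.2). Both rules can act only on events that come to the team's notice. Section 3.1 also asks for onset and duration of each event, and a daily named item supports that dating.

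**Working it through.** **1. Match the two lists.** The seven usual effects in 3.3.1 against the prompts in 3.1:

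| 3.3.1 usual effect | 3.1 prompt |
|---|---|
| dizziness | dizziness |
| somnolence | somnolence |
| xerostomia | dry mouth |
| headache | headache |
| visual disturbances | blurry vision (narrower, but counted as a match) |
| peripheral edema | edema |
| abnormal gait | none |

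The count of seven prompts in 3.1 is reproduced. Matched: 6 of 7. Unmatched: abnormal gait. The seventh prompt, nausea, is not listed in 3.3.1. None of the four effects put above 10% (fatigue, ataxia, tremor, weight gain) is prompted; ataxia is the one related to gait.

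**2. Identify the right comparison.** Because Table 1 has adverse event assessment every day and the diary issues reminders, an unprompted effect still has a daily opportunity to be recorded. The contrast is a daily named item against a daily open item plus a weekly call. The documents give no capture rate for either route, so the difference cannot be put into numbers.

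**3. Scale of possible events.** In a cross-over every completer takes pregabalin once. Section 2.4.8 requires 27 participants and aims to recruit 35. I assume that the percentages in 3.3.1 apply per patient for one treatment period.

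- Abnormal gait, stated only as below 15%: fewer than 0.15 × 27 = 4.05 to 0.15 × 35 = 5.25 patients.
- Ataxia, stated as above 10% and taken at 10%: 0.10 × 27 = 2.7 to 0.10 × 35 = 3.5 patients.

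The gait figure has no stated lower bound, so a range of assumed rates p is shown, with P(at least one) = 1 − (1 − p)^n:

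| p | expected, n = 27 | P(≥1), n = 27 | expected, n = 35 | P(≥1), n = 35 |
|---|---|---|---|---|
| 2% | 0.54 | 0.42 | 0.70 | 0.51 |
| 5% | 1.35 | 0.75 | 1.75 | 0.83 |
| 10% | 2.70 | 0.942 | 3.50 | 0.975 |
| 15% | 4.05 | 0.988 | 5.25 | 0.997 |

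These are events that may occur. They are not estimates of events missed.

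**4. Effect of one added prompt.** Prompts: 7 + 1 = 8. Usual effects asked about by name: 6 of 7 becomes 7 of 7. Burden: 28 days × 2 periods = 56 answers per patient, or 10 weeks × 7 = 70 if the prompts also run through the washout. No sample size or power figure changes.

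**The case against.** The strongest reply is that these effects are already covered. Patients are educated about them, reminded daily to complete an entry open to any adverse event, and telephoned weekly. Dizziness is prompted and overlaps with unsteadiness. Section 3.1 defines an adverse event broadly and treats relationship to the drug as a separate descriptor, so a patient need not blame the drug to report. This stands, and it rules out two inferences that a reader might draw: that gait problems go uncollected, and that the weekly call is the only other chance to report them. It does not remove the difference between being asked about walking and having to think of it. Section 3.1 calls the open report required and 2.4.3 calls it voluntary; either way the patient must raise the symptom.

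A second reply is that nothing obliges the prompts to mirror 3.3.1. Nausea shows that the list was not simply copied from it, and the prescribing information is an appendix not available here. That is fair: the omission is a design choice, not a contradiction.

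Third, diary data are reviewed only about weekly, so a new prompt would seldom speed the response within a seven-day titration. This also stands; the gain is mainly in capture and dating.

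Last, the dose rule applies to any grade 2 event whatever its cause, so asking people with painful feet about walking may bring disease-related reports that lower the dose. Table 1 provides no baseline gait assessment to judge them against. This is a real but modest cost.

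**Conclusion.** The point holds as a minor safety-collection gap: one of the seven usual effects, and the related ataxia, lack a named daily prompt, so recording of new unsteadiness may be somewhat weaker than recording of the other six. That patients would attribute unsteadiness to their neuropathy is a plausible assumption; the inclusion criterion concerns pain, and no section addresses balance.

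A reader might go further and infer that a known number of events will be missed, or that the pregabalin–placebo comparison is distorted. The documents support neither. The expected counts describe occurrence, and without a capture rate the shortfall cannot be computed. Collection is the same in both blinded periods, and nothing links it to the slope comparison that forms the primary outcome. Confidence is high in the list mismatch and moderate in its practical importance.

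**What to change.** Add one item to the daily prompts in 3.1, in both treatment periods: 'unsteadiness or trouble walking, new or worse than before this treatment period'. Leave the other seven prompts, the open entry and the weekly calls as they are.

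The cost is one diary setting and a one-line edit, with no new visit, staff or procedure. Each patient answers one more short item a day, and a few more grade 2 reports may lead to dose reduction. The 'new or worse' wording limits reports of existing foot trouble but will not remove them.

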2.3.2 Exclusion Criteria

Subjects will not be enrolled if any of the following criteria exist:

1. Hypersensitivity to pregabalin.
2. Current treatment with pregabalin.
3. CIPN that may be associated with previous treatment with a vinca alkaloid (e.g. vincristine, vinblastine), or current treatment with a vinca alkaloid.
4. History of diabetes mellitus or a neurological disorder with any previous signs of distal symmetric polyneuropathy.
5. Moderate to severe renal failure (Clcr < 30mL/min).

6. ALT (SGPT) or AST (SGOT) > 3 times the upper limit of normal.
7. Planned surgeries or radiation treatment within 10 weeks following study inclusion.
8. Inability to complete pain self-report.
9. Pregnancy or lactation
10. Patients with seizure disorders treated with anticonvulsants
11. Current participation in a trial with another investigational agent, unless co-enrollment is approved by the PIs of both studies.
12. Concomitant medication as follows:
 - Subjects treated with gabapentin or other anticonvulsant for neuropathic pain will be required to taper the medication and discontinue for at least 2 weeks prior to study initiation.
 - Patients on antidepressant treatment for pain or depression (TCAs, SSRI, SNRIs etc. will be allowed to continue their medications provided they have been on a stable dose for at least 4 weeks before study initiation. No dose regimen changes of antidepressants will be allowed during the study period.
 - Patients on around-the clock opioid treatment (including tramadol) will be allowed to continue their medication provided they have been on a stable dose for at least 4 weeks before study initiation. The maximum allowed dose of opioid will be equivalent to 60mg oral morphine sulphate. Patients with higher doses will be required to taper down their opioid dose to maximum 60mg oral morphine equivalent, and continue on stable dose for 4 weeks before enrollment in the study. PRN short-acting opioids for painful CIPN treatment will not be allowed. Patients receiving PRN short-acting opioids (with or without acetaminophen) for pain other than CIPN will be allowed up to 4 daily doses, with daily recording of analgesic consumption.
 - Treatment with NSAIDs will be discontinued at least 2 weeks before study initiation. However, low-dose aspirin (≤ 325 mg/day) will be allowed.

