2.4.2 Pre-Study Period

At the screening visit, after obtaining signed informed consent, we will collect patient demographic data including details on cancer type and status, chemotherapy regimen(s) and cumulative doses, history of chronic pain, concomitant diseases and medication, and duration of painful CIPN. A blood sample for CMP will be obtained for determining serum creatinine concentration and liver transaminases (ALT and AST). If subject's lab tests results are available within the past 30 days, we will utilize these without the need of obtaining new renal and hepatic function tests. In addition, the patients will complete the following questionnaires: Brief Pain Inventory (BPI), Neuropathic Pain Symptom Inventory (NPSI), and Depression Anxiety and Positive Outlook Scale (DAPOS). Average and maximum daily pain intensity in the past week will be recorded as baseline pain intensity measure.

The subjects' extremities will be mapped for spontaneous pain, and response to the following sensory stimulation: cold (20°C Thermal Roller, Somedic), warm (40°C Thermal Roller, Somedic), pinprick (# 5.88 Semmes-Weinstein monofilament, 60mN target force, North Coast) and brush (SenseLab 0.5 brush, Somedic) (Finnerup, Sorensen et al. 2007). The probability of neuropathic pain will be graded as possible, probable, or definite according to Treede et al. criteria (Treede, Jensen et al. 2008). The results of sensory mapping will provide the information for the criterion on presence of any objectively tested positive or negative neurological signs in the painful territory. Photographs of the mapped extremities will be taken (in a way not to include any part of the subjects' face or other identifying information), for accurate reproduction of areas of sensory disturbance.

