Patients will complete an electronic diary with daily report of their average and maximum daily pain intensity, recorded every evening before bedtime. The percentage of pain reduction for primary outcome will be assessed from the difference between baseline average pain intensity and the average pain intensity of last 5 days of treatment (day 24-28), on 0-10 NRS.

Secondary efficacy outcomes will include: 1) The difference between baseline maximum pain intensity and the maximum pain intensity of the last 5 days of treatment, on 0-10 NRS; 2) The proportion of patients achieving 50% or more pain relief with pregabalin vs. placebo treatment; 3) Difference in Pain Severity and Pain Interference scales of the BPI, assessed at baseline and day 28 of treatment. The daily use of rescue analgesia (oral acetaminophen) will also be recorded.

Table 1. Data assessment schedule

Required Assessments	Screening and Enrollment Baseline Visit	Week 1a	Week 2a	Week 3a	Week 4a	End of Treatment A (Day 28 +/- 2)	Wash-out	Study crossover visit	Week 1b	Week 2b	Week 3b	Week 4b	End of Study Visit (Day 30 +/- 3)
Study visits	Visit1 (a/b)*					Visit2		Visit3					Visit 4
Informed consent	✓												
Pregnancy (urine Hbhcg) test for women	✓												
Comprehensive Metabolic Panel (CMP) blood test**	✓					✓							✓
Inclusion/exclusion criteria	✓												
Randomization	✓												
Demographic data collection	✓												
Sensory Mapping	✓					✓		✓					✓
BPI questionnaire	✓				✓			✓				✓	
NPSI questionnaire	✓				✓			✓				✓	
DAPOS questionnaire	✓				✓			✓				✓	
SPI questionnaire	✓				✓			✓				✓	
QST	✓							✓					
CPM	✓							✓					
Dispense study drug	✓							✓					
Pain intensity 0-10 NRS	✓	daily	daily	daily	daily			✓	daily	daily	daily	daily	✓
Adverse Event assessment		daily	daily	daily	daily				daily	daily	daily	daily	✓
Telephone communication		weekly	weekly	weekly	weekly				weekly	weekly	weekly	weekly	
Blinding questionnaire***		✓											
Pill count								✓					✓
Blood sample (PK)						✓							✓
Skin biopsy (optional)													✓

*Visit 1 may be conducted over 2 visits to complete all assessments if required for subject tolerability or convenience

** A blood sample for CMP will not be obtained if recent (<30 days) results are available.

*** Blinding questionnaire to be administered via EMA device on Day 5 of study drug treatment

Subject Blinding Perception

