3.2 Premature Discontinuation

If a subject chooses to discontinue treatment during the first treatment phase, he/she has the possibility either to withdraw from the study, or to continue the second phase of the study after a 2 week washout period.

Subjects will be withdrawn if they undergo a major surgery during the study period (any surgery that requires 2 or more days of hospitalization).

Subjects will be withdrawn from the study if during the study period they are placed on chemotherapy regimen that includes a taxane, a platinum compound or a vinca alkaloid.

Subjects will be withdrawn from the study if they require an increase in their other analgesic drugs, including chronic around-the-clock opioid dose; or need more than 4 PRN daily doses of a short-acting opioid.

Subjects will be withdrawn from the study in case of any of the following adverse events:

- Angioedema
- Hypersensitivity
- Suicidal behavior or ideation
- Peripheral edema in patients with New York Heart Association (NYHA) Class III or IV heart failure (in non-cardiac patients the peripheral edema due to pregabalin has not been associated with cardiovascular complications).

Subjects will be withdrawn if they experience any Grade 3 or higher adverse effect, if the investigator decides that discontinuation is in the best interest of the subject, or the subject requests withdrawal from the study.

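### Seven symptoms are prompted daily during treatment, but none is graded before the first dose of either period, so new or worsened events cannot be separated from symptoms already present

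*Combined protocol and SAP*

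**What the plan says.** Section 3.1 defines an adverse event as "any unfavorable medical occurrence in a human subject including any abnormal sign, symptom, or disease". The definition sets no condition on when the symptom began or whether it got worse. The same section states: "Patients will be prompted to report seven specific adverse events". The seven are somnolence, dizziness, edema, nausea, headache, dry mouth and blurry vision, and the prompt comes daily on the study smartphone.

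In Table 1 (section 2.4.3), the row "Adverse Event assessment" is marked daily in weeks 1 to 4 of each period and once at the end-of-study visit. The cells for the baseline visit, the washout and the crossover visit are empty. Screening (section 2.4.2) collects "history of chronic pain, concomitant diseases and medication, and duration of painful CIPN", along with questionnaires, but schedules no grade for any of the seven symptoms.

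Two rules act on the adverse event record. The dose rule in 2.4.3 begins "In case of any grade 2 adverse events" and steps the patient back to the dose used before the most recent increase. Section 3.2 states: "Subjects will be withdrawn if they experience any Grade 3 or higher adverse effect"; section 2.4.3 has a matching withdrawal rule. None of these texts mentions the patient's state before dosing.

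**The concern.** The patients have had cancer treatment, and some take other drugs with effects on the nervous system: "Patients on around-the clock opioid treatment (including tramadol) will be allowed to continue their medication" (2.3.2), and stable antidepressants are allowed too. Some may already be drowsy, dizzy or nauseated, or have a dry mouth, before the first capsule. The documents do not say how many.

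Without a graded entry before dosing, three things are lost. A symptom that was there all along looks the same as one that began on treatment. Worsening from grade 1 to grade 2 cannot be shown, because the starting grade is unknown. And a symptom that persists from period 1 through the taper and washout looks the same as one that starts in period 2. What is at stake is how clearly the side-effect profile can be described, and whether staff apply the grade 2 and grade 3 rules consistently to patients who arrive with symptoms.

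**Working it through.** **Figures in the plan.** The documents give no adverse event comparison, safety sample size or background symptom rate, so there is no safety figure to reproduce. The stated 27 participants (35 recruited) serve the primary slope comparison and do not depend on this point.

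**Schedule against definition.** The prompts begin in week 1 of each period. The definition accepts any abnormal symptom. No graded entry exists at Visit 1 or at Visit 3. On the text, a symptom present before dosing and still present in week 1 can be recorded as an event in that period.

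**Effect on tabulated proportions.** Let b be the share of patients with the symptom before dosing, counted in both periods, and p the rate of new events among the rest.

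- Observed rate in a period = b + (1-b)p
- Observed risk difference = (1-b)(p on pregabalin - p on placebo)

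Example, all three inputs assumed: b = 25%, p = 40% on pregabalin and 20% on placebo.

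- Pregabalin: 0.25 + 0.75 x 0.40 = 0.55
- Placebo: 0.25 + 0.75 x 0.20 = 0.40
- Risk difference: 15 points instead of 20 (0.75 x 20)
- Ratio: 0.55/0.40 = 1.375 instead of 2.0

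Range over b, with p = 15% on pregabalin and an assumed 5% on placebo. Section 3.3.1 gives 15% as the upper limit for six of the seven prompted symptoms (nausea is not in that list).

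| b (assumed) | Pregabalin | Placebo | Risk difference | Ratio |
|---|---|---|---|---|
| 0% | 15.0% | 5.0% | 10 points | 3.00 |
| 10% | 23.5% | 14.5% | 9 points | 1.62 |
| 20% | 32.0% | 24.0% | 8 points | 1.33 |
| 30% | 40.5% | 33.5% | 7 points | 1.21 |
| 50% | 57.5% | 52.5% | 5 points | 1.10 |

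**Within-patient view.** A stable symptom gives a patient an event in both periods. That is a concordant pair: it adds no false difference and no information. With 27 patients, 15% v 5%, and new events independent between periods, the expected discordant pairs at b = 0 are 27 x 0.15 x 0.95 = 3.85 (pregabalin only) and 27 x 0.05 x 0.85 = 1.15 (placebo only). At b = 30% both are multiplied by 0.70, giving 2.69 and 0.80.

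**How often the definitional question would come up.** If a share g of 35 patients has a grade 2 symptom before dosing, the expected number is 35g and the chance of at least one is 1 - (1-g)^35. For assumed g of 3%, 5% and 10% this gives 1.1, 1.8 and 3.5 patients, and 66%, 83% and 98%. These count patients for whom the documents leave the answer open. They do not count dose reductions.

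**The case against.** Four points can be made in the plan's defence.

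1. **Much is already recorded.** Section 3.1 says: "The description of the adverse experience will include the time of onset, duration, severity, etiology, relationship to the study drug". A symptom that predates treatment could be entered with an early onset and no relationship to drug. Concomitant diseases are taken at screening, weekly calls ask about adverse events, and events are tracked until they resolve. This stands in part: some existing symptoms would be recognised. But onset before the first prompt depends on recall, and no field supplies a starting grade. The grade 2 and grade 3 rules do not refer to these fields.

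2. **Recording may run through the washout.** Section 3.1 can be read as daily prompting over the whole study, which would give a record before period 2. Table 1 leaves the washout blank, and on either reading nothing precedes period 1.

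3. **There is no safety comparison to dilute.** This stands for formal testing. Section 2.4.7 plans only pain and predictor analyses, and the safety output named in 3.5 is a summary of toxicities. The dilution concerns descriptive tables or a later comparison.

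4. **The dose rule presupposes an escalation.** This also stands. A reader might infer that a patient with an existing grade 2 symptom triggers the rule on day 1, is held at a low dose, and lowers mean exposure across the trial. The documents do not support that. The rule returns the patient to the dose before the last increase, and on day 1 there has been no increase and there is no earlier dose. The documents also give no background rate from which a loss of dose could be calculated. What remains is that after an increase the text does not say whether a symptom already present counts.

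**Conclusion.** The gap is real but minor. No graded pre-dose record of the seven symptoms is scheduled for either period, and the definition has no new-or-worse condition. Any tabulated pregabalin-placebo risk difference therefore shrinks by the factor (1-b). In the example this is 15 points instead of 20, and a ratio of 1.4 instead of 2.0. The factor rests on two assumptions: existing symptoms are reported in both periods, and new events arise at rate p among the other patients. The value of b is not in the documents, so the size is illustrative.

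A reader might go further and infer that the safety comparison is biased. It is not biased by stable background symptoms, since these fall in both periods and create no spurious difference. Nor is a planned test weakened, because none is planned. The primary analysis and its sample size are not shown to be affected. The definition in 3.1 and the rules in 2.4.3 and 3.2 do not state opposite things; together they leave open whether a symptom present before dosing counts.

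**What to change.** - Add one entry of the same seven smartphone items, with severity, at Visit 1 before the first dose and at Visit 3 before the period-2 dose. Mark both in the adverse event row of Table 1.
- State in 3.1 that events will be tabulated by treatment as new or worse than the entry for that period. Among patients free of the symptom at entry, this removes the dilution.
- Reconcile 2.4.3, 3.1 and 3.2 on whether a symptom already present before dosing counts as an adverse event for the grade 2 and grade 3 rules. The sponsor decides which way.

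The cost is about a minute of patient time at each of two visits that already exist, on a device the study already supplies, plus short text edits. The entry has to be made prospectively, because a starting grade cannot be reliably recovered later.
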